Vaping sessions will take place after collecting biospecimens and completing questionnaires on sociodemographics, tobacco use history, and dependence on ECs and cigarettes. Guided by study staff, participants will take two puffs of each of the 10 study conditions (5 freebase nicotine fractions \times 2 nicotine concentrations) using the study EC device, followed by a 10-minute washout period between conditions. During the washout period, participants will be instructed to rinse their mouths and spit three times with room-temperature water before sampling the next preparation to minimize carryover effects. The washout period was deemed sufficient based on an arterial study showing a return to baseline plasma nicotine levels 40 minutes following a 10-puff vaping session (hence, 4 minutes are needed for nicotine levels to return to baseline after each puff).²² Participants will be provided pre-filled and weighed e-liquid pods in random order. Participants will be instructed to inhale for at least 1 second for each puff, but other puffing parameters (i.e., flow rate, maximum puff duration, puff volume, rate of exhalation) will not be controlled.

After each condition, participants will complete General Labeled Magnitude Scale (gLMS)¹⁴ and Labeled Hedonic Scale²³ to rate the degree of liking or disliking of sensations and the strength of sensory attributes of e-liquids including throat hit, smoothness, harshness, sweetness, and bitterness. Participants will also rate overall acceptance on a tobacco industry-designed thermometer scale (from 0 "the very worst" to 100 "the very best", with 50 indicating "indifferent").²⁴ Drug Effects/Liking Questionnaire,²⁵ the modified Cigarette Evaluation Questionnaire (mCEQ), and the adapted version of behavioral intentions for continued use (from 1 "extremely unlikely" to 7 "extremely likely")²⁶ will also be collected to assess subjective responses to ECs (e.g., reward, satisfaction).²⁷

All study visits will take place at the OSUCCC's Center for Tobacco Research, where participants will complete a consent form, screening procedures, vaping sessions, and online questionnaires and surveys on a tablet.

C. Recruitment

1) Number of Participants

A total of 150 participants will be recruited, including young adult e-cigarette (EC) users with minimal or no history of smoking (n=75) and older adult smokers (n=75).

2) Participant Population

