The primary goal of the study is to identify a nicotine fraction limit that is appealing to smokers with a minimal appeal to young adult EC users. Generalized linear mixed models will be employed for measures of appeal (e.g., industry thermometer rating and sensory appeal metrics). Models will include demographic and smoking history as covariates, random effects for subject, main effects for user group (smokers vs. EC use), FB fraction (numeric), and concentration (categorical), and interaction effects between smoking group and each of the condition parameter variables (i.e., FB fraction and concentration). A significant interaction between smoking group and a condition parameter variable would indicate that the variable differentially affects appeal between the two user groups. Because of multiple measurements tested, we will assume a significance threshold of $p=0.01$. Conservatively, considering 120 participants, a correlation of 0.5, and $\alpha=0.01$, a two-sided paired t-test achieves 80% power to detect an effect size of 0.32 standard deviations of the measurement for the concentration main effect. For FB fraction, with 120 subjects, the model achieves 80% power to detect a slope of 0.31, considering $\alpha=0.01$. We estimate the power for the categorical interactions by pairwise comparisons of the two interacting groups (with two 2-level variables there are a total of 4 groups) and adjust the p-value to account for the 6 possible pairwise comparisons ($0.01/6=0.0017=p$). With 30 samples per group, a two-sided, two-sample t-test achieves over 80% power to detect a 1.7-fold difference between any of the two groups in the interaction term, considering $\alpha=0.0017$ and coefficient of variation=0.5. For interactions with FB fraction, group sizes of 60 achieve 80% power to detect a difference in slopes of 0.43, considering $\alpha=0.01$. Interactions between condition parameter variables will also be explored. Since our goal is to find combinations of the condition parameter that are appealing to smokers but not young adult EC users, we will compare condition combinations directly to identify the condition parameter combinations that result in the largest difference in appeal between

the two user groups. Carryover effects will be explored by estimating the interaction of a given condition with the preceding treatment and period effects tested by the interaction of treatment with order.

III. Data and Safety Monitoring Plan

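### The carryover and period checks are specified only as interactions, so a null result would say little about additive carryover or drift over the visit

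*Combined protocol and SAP*

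**What the plan says.** All references are to the combined protocol and SAP.

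- **II.B Study Procedures.** In one visit, "participants will take two puffs of each of the 10 study conditions", "followed by a 10-minute washout period between conditions". Mouth rinsing takes place "before sampling the next preparation to minimize carryover effects". Allocation is described as follows: "Participants will be provided pre-filled and weighed e-liquid pods in random order". The washout is justified by a study of plasma nicotine after ten puffs, scaled down per puff.
- **II.E Data Analysis, outcome model.** The fixed effects listed are covariates, user group, FB fraction as a number, concentration as a class variable, and "interaction effects between smoking group and each of the condition parameter variables". There is a random subject effect. Neither order nor the preceding pod appears in the list.
- **II.E Data Analysis, checks.** "Carryover effects will be explored by estimating the interaction of a given condition with the preceding treatment", with "period effects tested by the interaction of treatment with order". The model in which these interactions would be fitted is not described further.

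**The concern.** In a ten-period crossover within one visit, the simplest way for a washout to fail is additive. A strong pod leaves nicotine or throat irritation behind, and the next rating moves by some amount, whichever pod comes next. In model terms that is a main effect of the predecessor. The interaction of condition with predecessor asks a narrower question: does the size of that shift depend on the current pod?

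The period check has the same structure. A drift common to all conditions, such as accumulating nicotine, fatigue or adaptation, is a main effect of order. Treatment by order asks only whether the drift differs between treatments.

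The washout argument in II.B concerns plasma nicotine. It does not address throat irritation, although throat hit and harshness are rated after every condition. The blood sample described in II.B is a baseline sample to confirm abstinence. The analyses of order and predecessor are therefore the main planned evidence from the trial's own data on whether ten minutes sufficed, and a null result from them could be given more weight than it can bear.

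**Working it through.** **Inputs.** From II.E: alpha 0.01, 120 participants for power, correlation 0.5, detectable concentration effect 0.32 SD at 80% power. From II.B and II.C: 10 conditions in random order, 2 puffs each, 10-minute washout, 150 participants to be recruited. The carryover and drift sizes below are assumptions; the documents give none.

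**The plan's own figures.** The SD of a paired difference is SD × √(2(1 − 0.5)) = 1 SD. With n = 120, effect 0.32 and two-sided alpha 0.01, the noncentral t gives 81.1% power, which agrees with the stated 80%. The washout arithmetic also reproduces: 40/10 = 4 minutes per puff, and 2 × 4 = 8 minutes, below 10. II.E states no power for the carryover check.

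**Size of the interaction.** No condition follows itself, so there are 10 × 9 = 90 ordered pairs. If both conditions are coded as class variables, the interaction has 90 − 1 − 9 − 9 = 71 df. Each pair has about 120 × 9/90 = 12 observations (15 with 150 participants). If the predecessor main effect is not fitted separately, its 9 df join the interaction: 71 + 9 = 80 df.

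**Why the fitted interaction is blind.** Once current condition and predecessor are both in the model, a purely additive shift is absorbed by the predecessor term. Nothing is left for the interaction, so its F statistic keeps its null distribution.

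**Simulation, carryover driven by concentration.** Setting: 120 participants, random order, correlation 0.5, alpha 0.01, subject and current-condition effects fitted. The next rating shifts by 0.20 SD after a 50 rather than a 20 mg/mL pod.

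| Test | Detection |
|---|---|
| Condition × predecessor, main effects fitted (71 df) | about 0–1% |
| All predecessor terms pooled (80 df) | about 19–22% |
| Concentration × preceding concentration, no predecessor main effect (2 df) | about 95–96% |
| Main effects of preceding concentration and FB fraction (2 df) | about 95–97% |

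The ranges are across repeat simulations. At 0.15 SD the first, second and fourth rows become about 1%, 5% and 68–69%.

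**Simulation, carryover driven by FB fraction.** Setting: 150 participants, 300 replicates, with a shift rising linearly from 0 after a 5% pod to λ after an 85% pod.

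- Main effects fitted, λ = 0.32, 0.5 and 1.0 SD: the 71-df test rejects 0.7%, 0.3% and 2.0%. The 1-df numeric FB × preceding-FB test rejects 1.0%, 0.7% and 0.7%. The blindness is therefore not just a matter of too many degrees of freedom.
- Predecessor main effect omitted, λ = 0.32: 45% (80 df) or 98% (numeric, uncentred).
- Predecessor main effect tested, λ = 0.32: 96% (9 df, class) or 99.7% (1 df, numeric).

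**Common drift over the visit (150 participants).** For a linear drift of 0.32 SD, treatment × order rejects 0.3%, predecessor main effects about 1%, and a linear main effect of order 99.7%. For 1.0 SD, treatment × order rejects 1.7%.

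**Bias in within-person contrasts.** If the current pod is 50 mg/mL, 4 of the other 9 conditions are 50; if it is 20 mg/mL, 5 of 9 are. The difference is −1/9, and a predecessor exists in 9 of 10 positions, so the bias is −1/9 × 9/10 = −1/10 of the carryover. For 0.20 SD that is −0.02 SD. The FB slope behaves alike: simulated bias was about −0.03 for λ = 0.32 and −0.10 for λ = 1.0.

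**Between-group comparisons.** As an extreme case, suppose the 0.20 SD carryover occurs in one user group only. That group's mean rating then shifts by 0.20 × 5/9 × 9/10 = 0.10 SD for 20 mg/mL pods and by 0.20 × 4/9 × 9/10 = 0.08 SD for 50 mg/mL pods. The difference in appeal between groups at any one condition moves by 0.08–0.10 SD, and the group-by-concentration contrast by 0.02 SD.

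**The case against.** The strongest counter-argument is that II.E never writes down the carryover model. Its list of main effects describes the outcome model. An analyst who enters the interaction without the predecessor main effect would pick up additive carryover under the interaction label, with detection as high as 95–98% in some codings. An analyst who keeps the hierarchy would see the predecessor estimate in the output, although no test of it is planned. Carryover whose size depends on the current pod could also show in the interaction. All this stands. It rules out a statement that the plan cannot detect carryover, but it leaves a check whose answer depends on an unstated choice.

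It is also fair that random order protects the within-person contrasts: 0.02 SD is small beside the 0.32 SD the plan is powered to detect. The simulated shift lies in a term that the 2-df test contains, which favours that test. The 71-df result does not depend on this, because it follows from the model structure.

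A reader might go further and infer three things that the documents do not support.

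- *A failed washout would be reported as absence of carryover.* II.E calls the check exploratory and states no pass rule or reporting consequence.
- *This is the only empirical check.* Treatment by order is planned as well, though it has the same gap for additive effects.
- *The primary results are materially biased.* The one-tenth arithmetic says otherwise for pooled within-person effects.

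**Conclusion.** The point holds as a weakness of the check. With the hierarchy respected, the planned carryover test has only its nominal rejection rate of about 1% against additive carryover of any size, and treatment by order does no better against a common drift. With the hierarchy broken, detection of a 0.20 SD carryover at 120 participants is anywhere from about 19% to about 95%. In neither case does a null result, taken from the text as written, say much about whether the washout was adequate.

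The consequence for the estimates is limited: about one tenth of the carryover in pooled within-person contrasts, and more for between-group levels only if carryover differs between smokers and EC users. The documents neither suggest nor exclude such a difference. It deserves a term because II.E intends to compare condition combinations between the groups.

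The percentages rest on assumed carryover sizes, a correlation of 0.5, simple random order and normal errors. The blindness of the hierarchical interaction test to additive carryover does not depend on the sizes assumed. The change should be made before analysis; it does not call the design into question.

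**What to change.** Replace the sentence on carryover and period in II.E with a stated model:

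1. **Carryover.** Add main effects of the immediately preceding pod's concentration (20/50) and FB fraction (numeric), and test them jointly on 2 df using positions 2–10.
2. **Period.** Add a main effect of order and test it. The predecessor terms cannot do this job, because a shift that is equal after every pod, or that accumulates, appears only as an order effect.
3. **User group.** Add the interactions of the predecessor terms and of order with user group.
4. **Secondary.** Keep condition × predecessor and treatment × order as exploratory, fitted with the corresponding main effects in the model.
5. **Reporting.** Give the condition estimates with and without these terms, whatever the tests show, so that the choice of estimate does not hang on a preliminary test.

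The cost is wording and a few model degrees of freedom: 2 for the predecessor, 1 for order if linear, and as many again for the group interactions, so 6 in all. Each participant's first rating does not contribute to the carryover test. No new data are needed beyond the pod order, which the planned treatment-by-order test already requires.

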In the proposed study, a sample of young adult (21-24 years) exclusive EC users with no or minimal history of smoking (n=75) and older adult (25-50 years) smokers (n=75) will complete a single-visit, double-blinded, within-subject randomized crossover trial. Participants will vape e-liquids containing varying freebase (FB) nicotine fractions (5, 25, 45, 65, 85%) at 20 or 50 mg/mL concentrations. The FB fractions were selected to cover a wide range with the lower end consistent with JUUL and disposable pod-based ECs that are popular among youth¹¹ and the higher end resembling early ECs that were FB nicotine-based and less appealing to young people. Each of the 10 conditions will be tested in a 2-puff session, followed by rating the appeal and sensory attributes, with a 10-minute washout period between conditions. Previous studies used a similar study design to examine the appeal of EC flavors, nicotine concentrations, and interactive effects of flavor and nicotine.¹²⁻¹⁵ For example, in a study of young adult current EC users,¹² the sensory appeal of ECs decreased as nicotine concentration increased but was not affected by flavoring. Another study of current EC users or smokers reported higher ratings of appeal for salt nicotine vs. free-base nicotine across different flavors, and salt nicotine decreased perceived harshness more among never smokers than ever smokers.¹⁵ While these studies shed light on the effect of nicotine salts and concentration on the sensory experience of EC use, their design was limited in ability to evaluate the effect of granular fractions of nicotine salts. This study will fill the gap in the literature by examining the effect of five free-base levels of nicotine at two nicotine concentration levels and determining the 'sweet spot' level of free-base nicotine that can be tolerated by smokers but not by non-smokers.

B. Study Procedures

Participants will be screened initially through an online screener, which will be linked to our study advertisement and administered using REDCap. Eligible participants interested in participating will be scheduled for the study visit via phone or e-mail. Participants will be instructed that they must remain nicotine abstinent for 12 hours before their visit and will receive a reminder the evening before.

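### The appeal model has no session-position term, and the treatment-by-order interaction named as the period test does not target a drift common to all conditions

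*Combined protocol and SAP*

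**What the plan says.** II.E Data Analysis specifies a generalized linear mixed model for appeal. Besides demographic and smoking-history covariates it has "random effects for subject, main effects for user group (smokers vs. EC use), FB fraction (numeric), and concentration (categorical"), plus "interaction effects between smoking group and each of the condition parameter variables (i.e., FB fraction and concentration"). Session position, period and order are not among the terms.

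The same section ends with two checks. Carryover is to be explored through the interaction of a condition with the one before it, and the plan has "period effects tested by the interaction of treatment with order". It does not say how order is coded or whether an order main effect is fitted alongside.

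On the design, II.B Study Procedures says that participants "must remain nicotine abstinent for 12 hours before their visit" and that "Participants will be provided pre-filled and weighed e-liquid pods in random order". There are ten two-puff conditions in one visit, with 10 minutes between them. That interval is justified by a study "showing a return to baseline plasma nicotine levels 40 minutes following a 10-puff vaping session", followed by the inference "hence, 4 minutes are needed for nicotine levels to return to baseline after each puff".

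On power for the main question, II.E states that "group sizes of 60 achieve 80% power to detect a difference in slopes of 0.43" at alpha 0.01. The scale of that slope is not given.

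**The concern.** Ten ratings in about three hours, starting from abstinence, are a setting in which scores may move with time whatever is in the pod: relief of abstinence, satiation, throat fatigue or familiarity with the scales. Two things follow.

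First, a drift that is not modelled goes into the within-subject residual. The user-group by FB-fraction interaction, which carries the study's main question, is tested against that residual.

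Second, the diagnostic is aimed at something else. Treatment by order asks whether differences between conditions change over the visit. A shift that moves all ten conditions equally is a main effect of position, and the plan does not name that as the test. A null interaction could be written up as showing no period effect when there is one.

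**Working it through.** **Inputs from the plan (II.E):** correlation 0.5; two-sided alpha 0.01; 120 participants (60 per group) for power; slope difference 0.43. Planned enrolment is 75 per group (II.C). FB levels are 5, 25, 45, 65 and 85% at two concentrations, so there are ten ratings per person.

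**Assumption:** linear drift of D total SDs from first to tenth session. The documents give no value, so a range is shown.

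**Plan's own figure.** For concentration the SD of a paired difference is sqrt(2 × (1 − 0.5)) = 1 total SD. With n = 120 and an effect of 0.32, the noncentral t gives 81.1% power, against the stated 80%, so this reproduces. The 0.43 figure cannot be reproduced without its scale.

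**Variance inflation.** With total variance 1 and correlation 0.5, residual variance is 0.5. Positions 1 to 10 have population variance 8.25. Each participant gets every position once, so

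inflation = D² × (8.25/81) × (10/9) / 0.5

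D = 0.5, 1, 1.5 gives 0.057, 0.226, 0.509. If D is counted in residual SDs instead, the inflation is half: 3%, 11%, 25%.

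**Power for group by FB fraction (no random slopes).**

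Var(slope difference) = 2 × 0.5 × (1 + inflation) / (Sxx × n per group)

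Power = Φ(0.43/SE − 2.576)

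Sxx per person over ten ratings is 1.25 if FB is scaled by its 80-point range, 10 if per SD of FB, and 20 if per 20-point step. Example: range scale, 75 per group, D = 0: SE = sqrt(1/(1.25 × 75)) = 0.103, and Φ(4.16 − 2.58) = 0.944.

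| Scale of 0.43 | n per group | D = 0 | 0.5 | 1 | 1.5 |
|---|---|---|---|---|---|
| full 5–85% range | 60 | 87.5% | 85.2% | 78.4% | 67.6% |
| full 5–85% range | 75 | 94.4% | 93.0% | 88.2% | 79.2% |
| per SD or per step | 60 or 75 | ~100% | ~100% | ~100% | ~100% |

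Simulation on the range scale agrees (1,500 runs). At 75 per group, power without position is 94.3%, 92.9%, 88.1% and 79.9%; with position it is 94–95% throughout.

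**Bias.** In simulation with random order, the mean error of the group-by-FB estimate was at most 0.005 residual SD. Type I error without position was 0.95% with no drift and 1.5% at D = 1.5 (2,000 runs); with position it was 0.85% and 1.3%. Both are close to 1%.

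**What each test detects.** Pure drift, n = 120, alpha 0.01, percentage of runs rejecting:

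| Test | D = 0.25 | D = 0.5 |
|---|---|---|
| Linear position main effect | 91% | 100% |
| 10-level position main effect | 58–59% | 100% |
| Treatment × order, order main effect fitted | 0.6–1.5% | 0.3–0.9% |
| Treatment × order alone, numeric, centred | 1.6% | 1.6% |
| Treatment × order alone, numeric, uncentred | 73% | 100% |
| Treatment × order alone, categorical | 10% | 85% |

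The outcome of the planned test thus turns on coding that the plan does not state. If order means the whole sequence, ten conditions allow 10! sequences, most participants will have a unique one, and the term is close to saturated.

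**Washout wording.** 40/10 = 4 minutes per puff, or 8 for two puffs, which is inside the 10-minute interval; the arithmetic is right. The step assumes that return time is proportional to puff count, and one observation after ten puffs does not establish that.

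**The case against.** The plan does not ignore period. It schedules both a period and a carryover check, and a conventional fit of an interaction includes its main effects, so position would probably be estimated there. That is fair: the gap is that the main effect is neither named as the test nor placed in the primary model.

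A reader might infer that the omission biases the comparison between user groups. It does not: pods are in random order, and each participant contributes every position, so a common drift does not favour any condition or group-by-condition contrast.

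A reader might also infer that the trial is underpowered. The documents do not support that. The loss appears only if 0.43 spans the full FB range, and that scale is weakly supported: it gives 87.5% rather than the stated 80% for 0.43, and 99.7% for the companion slope of 0.31. Reading 0.31 per SD of FB, with one observation per subject and unit residual SD, gives about 78%, nearer the plan. On the per-SD or per-step scale there is essentially no loss. Even on the range scale, the loss at 75 per group is about 1 point at 0.5 SD of drift and 6 points at 1 SD.

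Finally, the washout inference might be read as evidence of carryover. It is not. The 40-minute figure concerns plasma nicotine, the outcomes are sensory and appeal ratings, and the protocol also has participants rinse between conditions.

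**Conclusion.** The point holds as a minor one. The listed model has no position term, and treatment by order is the wrong test for a drift common to all conditions: it is near its 1% level when the order main effect is fitted or the coding is centred, and hard to interpret otherwise. The main consequence is a diagnostic that could be reported as clean when drift is present.

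The cost to the primary analysis is precision only. Within-subject variance rises by about 6%, 23% or 51% for assumed linear drift of 0.5, 1 or 1.5 total SD at correlation 0.5. Power for 0.43 at 75 per group goes from 94% to 93%, 88% or 79% if 0.43 spans the full FB range, and is essentially unchanged on the other two scales. These figures illustrate sensitivity; they are not an expected loss, because neither the drift size nor the slope scale is in the documents.

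The washout inference is a separate wording note and carries no weight in this conclusion.

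**What to change.** - Add session position as a fixed main effect to the primary appeal model, with 10 levels, or linear if stated in advance. Linear has more power against a straight-line drift; 10 levels do not assume that shape.
- Define the period test as the test of that main effect.
- Keep treatment by position as a sensitivity check, with the position main effect included and the coding stated.
- State the scale of the 0.43 and 0.31 slopes, so that the power statements can be checked.
- As a wording note, reconcile the washout rationale in II.B with the cited 40-minute figure and drop the per-puff division unless it can be supported. No washout length is proposed here.

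Cost: 9 degrees of freedom out of about 1,500 observations (150 × 10). With no drift, the variance of the group-by-FB estimate rises by about 0.8% (simulated ratio of squared standard errors without to with position 0.992 at 60 per group). Position is known from the order in which pods are given, so no new data are needed.
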